APPENDIX 2. PARTIAL DATE CONVENTIONS

Imputed dates will NOT be presented in the listings.

ALGORITHM FOR PRIOR / ACTIVE MEDICAL HISTORY, SURGERIES AND PROCEDURES

Partial date to be imputed as:

Start date	Earliest possible date	first day of month if day unknown or 1 st January if day and month are unknown
Stop date	Latest possible date	last day of month if day unknown or 31 st December if day and month are unknown, if not resulting in a date later than the date of subject's death. In the later case the date of death will be used for imputation.

General rules:

If stop date < trial med start date, assign as prior

If stop date >= trial med start date and start date <= end of treatment, assign as concomitant

If stop date >= trial med start date and start date > end of treatment, assign as post Treatment

If Missing stop date: (Rules 2)

If stop date is missing could never be assumed as prior

If start date <= end of treatment, assign as concomitant

If start date > end of treatment, assign as post treatment

If Missing Start date: (Rules 3)

If stop date < trial med start date, assign as prior

If stop date >= trial med start date, assign as active

Cannot be assigned as 'post treatment'

START DATE	STOP DATE	ACTION
Known	Known	General rules
	Partial	General rules
	Missing	Rules 2
Partial	Known	General rules
	Partial	General rules
	Missing	Rules 2

Document: \\ieedc-nas01a:\Boehringer_Ingelheim\BI_695501\XXA39605\Biostatistics\Documentation\SAP\15-v2.0\BI 1297.12 SAP v2.0 31JAN2018.docx

Author:

Version Number:

2.0

Version Date:

31JAN2018

Template No: CS_TP_BS016 Revision 4

Reference: CS_WI_BS005

Effective Date: 01Apr2016

Copyright © 2009, 2010, 2012, 2016

All rights reserved.

The contents of this document are confidential and proprietary to reproduction is strictly prohibited.

Unauthorized use, disclosure or

Statistical Analysis Plan

START DATE	STOP DATE	ACTION
Missing	Known	Rules 3
	Partial	Rules 3
	Missing	Assign as concomitant

Algorithm for Treatment Emergence of Adverse Events:

START DATE	STOP DATE	ACTION
Known	Known Partial Missing	If start date < trial med start date or start date > trial med stop date +70 days, then not TEAE If start date >= trial med start date and start date <= trial med stop date +70 days, then TEAE
Partial, but known components show that it cannot be on or after trial med start date	Known Partial Missing	Not TEAE
Partial, could be on or after trial med start date	Known	Impute start date as earliest possible date, (i.e., first day of month if day unknown or 1st January if day and month are unknown), except if only day is missing and month and year of start date are the same as for trial med start date or if day and month are missing and year of start date is the same as for trial med start date. In the later cases, the trial med start date will be used for the imputation. If start date <= stop date, then: If stop date < trial med start date, then not TEAE If start date > trial med end date +70 days, then not TEAE If stop date >= trial med start date and start date <= trial med end date +70 days, then TEAE If start date > stop date, then: Consider the start date as Missing and apply the algorithms for missing start date
	Partial	Impute start date as above. Impute stop date as latest possible date (i.e., last day of month

Document: \\ieedc-nas01a:\Boehringer_Ingelheim\BI_695501\XXA39605\Biostatistics\Documentation\SAP\15-v2.0\BI 1297.12 SAP v2.0 31JAN2018.docx

Author:

Version Number:

2.0

Version Date:

31JAN2018

Template No: CS_TP_BS016 Revision 4

Reference: CS_WI_BS005

Effective Date: 01Apr2016

Copyright © 2009, 2010, 2012, 2016

All rights reserved.

The contents of this document are confidential and proprietary to reproduction is strictly prohibited.

Unauthorized use, disclosure or

START DATE	STOP DATE	ACTION
		if day unknown or 31 st December if day and month are unknown), if not resulting in a date later than the date of subject's death. In the later case the date of death will be used for imputation. If start date <= stop date, then: If stop date < trial med start date, then not TEAE If start date > trial med end date +70 days, then not TEAE If stop date >= trial med start date and start date <= trial med end date +70 days, then TEAE If start date > stop date, then: Consider the start and stop dates as Missing and apply the algorithms for missing start date
	Missing	Assumed TEAE
Missing	Known	If stop date < trial med start date, then not TEAE If stop date >= trial med start date, then TEAE
	Partial	Impute stop date as latest possible date (i.e. last day of month if day unknown or 31 st December if day and month are unknown), then: If stop date < trial med start date, then not TEAE If stop date >= trial med start date, then TEAE
	Missing	Assumed TEAE

Algorithm for Prior / Concomitant Medications:

Partial date to be imputed as:

Start date	Earliest possible date	first day of month if day unknown or 1 st January if day and month are unknown
Stop date	Latest possible date	last day of month if day unknown or 31 st December if day and month are unknown, if not resulting in a date later than the date of subject's death. In the later case the date of

Document: \\ieedc-nas01a:\Boehringer_Ingelheim\BI_695501\XXA39605\Biostatistics\Documentation\SAP\15-v2.0\BI 1297.12 SAP v2.0 31JAN2018.docx

 Author: Version Number: 2.0
 Version Date: 31JAN2018

 Template No: CS_TP_BS016 Revision 4
 Effective Date: 01Apr2016

Reference: CS_WI_BS005

Statistical Analysis Plan

		death will be used for imputation.
--	--	------------------------------------

General rules:

- If stop date < trial med start date, assign as prior
- If stop date >= trial med start date and start date <= end of treatment, assign as concomitant
- If stop date >= trial med start date and start date > end of treatment, assign as post Treatment

If Missing stop date: (Rules 2)

- If stop date is missing could never be assumed a prior medication
- If start date <= end of treatment, assign as concomitant
- If start date > end of treatment, assign as post treatment

If Missing Start date: (Rules 3)

- If stop date < trial med start date, assign as prior
- If stop date >= trial med start date, assign as concomitant
- Cannot be assigned as 'post treatment'

START DATE	STOP DATE	ACTION
Known	Known	General rules
	Partial	General rules
	Missing	Rules 2
Partial	Known	General rules
	Partial	General rules
	Missing	Rules 2
Missing	Known	Rules 3
	Partial	Rules 3
	Missing	Assign as concomitant

Document: \\ieedc-nas01a:\Boehringer_Ingelheim\BI_695501\XXA39605\Biostatistics\Documentation\SAP\15-v2.0\BI 1297.12 SAP v2.0 31JAN2018.docx

Author: Version Number: 2.0
Version Date: 31JAN2018

Template No: CS_TP_BS016 Revision 4
Effective Date: 01Apr2016

Reference: CS_WI_BS005

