16.1.1. ADVERSE EVENT SPECIFIC DERIVATION

16.1.1.1. Treatment Emergent Adverse Event

Treatment-Emergent Adverse Events (TEAEs) are defined as AEs that started or worsened on or after the first dose of trial medication and prior to the last date of trial medication + 10 weeks (70 days) inclusive.

There is one specific period of interest:

- Period 1 starts on the first administration day (Day 1 visit) and finishes prior to the visit date of Day 113 visit.

Period 1 Treatment-Emergent Adverse Events (P1 TEAEs) are defined as AEs that started or worsened on or after the first dose of trial medication during period 1 and prior to or at the last date of trial medication during period 1 + 10 weeks (70 days) inclusive.

Non-TEAEs will be classified as "Screening" if AE start date is strictly prior the first injection date. Non-TEAEs will

Document: \\ieedc-nas01a:\Boehringer_Ingelheim\BI_695501\XXA39605\Biostatistics\Documentation\SAP\15-v2.0\BI 1297.12 SAP v2.0 31JAN2018.docx

Author: Version Number: 2.0
Version Date: 31JAN2018

Template No: CS_TP_BS016 Revision 4
Effective Date: 01Apr2016

Reference: CS_WI_BS005

be classified as “Post treatment” if AE start date is strictly after the last injection date + 70 days.

See APPENDIX 2 for handling of partial dates for AEs. In the case where it is not possible to define an AE as treatment-emergent or not, the AE will be classified by the worst case, i.e., treatment-emergent in the period of the last injection of trial medication.

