16.1.2.2. Relationship to Trial Medication

A related AE is defined as a TEAE with the item “Causal Relationship between the event and the trial drug” ticked “Related” on the AE form of the eCRF according to the investigator.

TEAEs with a missing relationship to trial medication will be regarded as related to trial medication. If a subject reports the same TEAE more than once for the given period within that SOC/ PT, the TEAE with the worst case

Document: \\ieedc-nas01a:\Boehringer_Ingelheim\BI_695501\XXA39605\Biostatistics\Documentation\SAP\15
-v2.0\BI 1297.12 SAP v2.0 31JAN2018.docx

Author: Version Number: 2.0
Version Date: 31JAN2018

Template No: CS_TP_BS016 Revision 4
Effective Date: 01Apr2016

Reference: CS_WI_BS005

relationship to trial medication within that period will be used in the corresponding relationship summaries.

All drug related AEs will be listed.

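### Two cells of the SAP Appendix 2 treatment-emergence table count adverse events as treatment-emergent when their recorded dates already show that they are not

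*SAP*

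**What the plan says.** SAP section 16.1.1.1 counts an event as treatment-emergent if it started or worsened on or after first dose and "prior to the last date of trial medication + 10 weeks (70 days) inclusive". An event is a screening event "if AE start date is strictly prior the first injection date" and a post-treatment event "if AE start date is strictly after the last injection date + 70 days". The worst-case rule (count it as treatment-emergent) has a stated condition: "In the case where it is not possible to define an AE as treatment-emergent or not".

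Appendix 2 turns this into a table by type of start and stop date:

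- **Known start:** both limits are tested (first dose, and last dose + 70 days).
- **Partial start that could be on or after first dose:** the start is imputed to the earliest possible date. If the known parts match the month or year of first dose, it is set to the first-dose date instead.
  - *Known stop:* if the imputed start is after the stop, "Consider the start date as Missing and apply the algorithms for missing start date".
  - *Partial stop:* the stop is imputed to its latest possible date; if the imputed start is after it, "Consider the start and stop dates as Missing and apply the algorithms for missing start date".
  - *Missing stop:* assumed treatment-emergent, with no date test.
- **Missing start:** with a known or partial stop, not treatment-emergent if the stop is before first dose; with a missing stop, assumed treatment-emergent.

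The known-stop and partial-stop cells both carry the 70-day test.

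**The concern.** A rule for incomplete dates should fall back on the worst case only when the recorded parts leave the status open. In two cells the recorded parts settle it and the table returns the opposite answer.

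Treatment-emergent status feeds the adverse event summaries and the one secondary safety endpoint, the proportion of patients with drug-related events. Section 16.1.2.2 defines a related event as a treatment-emergent one and adds: "TEAEs with a missing relationship to trial medication will be regarded as related to trial medication". A screening event wrongly made treatment-emergent, with a blank causality field, would therefore count towards that endpoint.

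**Working it through.** The plan gives no figure to reproduce. The check is a trace of the table, using assumed dates.

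**Assumed patient.** First dose (Day 1) 15 Jun 2017. Last dose on Day 162, the last planned dosing day in the protocol Flow Chart: 15 Jun + 161 days = 23 Nov 2017. Window end: 23 Nov + 70 days = 1 Feb 2018.

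**Cell (a): partial start, partial stop.** Recorded start: 2017. Recorded stop: May 2017.

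1. The start year equals the first-dose year, so the start becomes 15 Jun 2017.
2. The stop becomes its latest possible date, 31 May 2017.
3. 15 Jun is after 31 May, so both dates are treated as missing.
4. Missing start and missing stop: assumed treatment-emergent.

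The latest possible stop is before first dose, so the event cannot have started on treatment. The neighbouring cells agree:

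| Recorded start | Recorded stop | Table result |
|---|---|---|
| 2017 | May 2017 | treatment-emergent |
| 2017 | 31 May 2017 | not treatment-emergent |
| missing | May 2017 | not treatment-emergent |

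Recording the start year, rather than nothing, changes a right answer to a wrong one. The partial/partial cell does contain a line excluding events that stopped before first dose, but only under the condition that the imputed start is on or before the stop. In this row the imputed start is never before first dose, so a stop that is both on or after that start and before first dose is impossible. The line cannot be reached.

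**Cell (b): partial start, missing stop.** Recorded start: March 2018. No stop.

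1. The earliest possible start is 1 Mar 2018, which is after 1 Feb 2018.
2. The cell makes no comparison: assumed treatment-emergent.

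A known start of 1 Mar 2018 with no stop is not treatment-emergent, and neither is March 2018 with a stop of April 2018. A start of February 2018 with no stop is different: 1 Feb is inside the window, the status is open, and counting the event is right.

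**Whole table.** I coded the table as written and ran it over all missing, year-only and month-level start and stop patterns for 2016 to 2018, for first doses of 15 Mar and 15 Jun 2017. Among internally consistent records, contradictions arose only in these two cells. With the two changes under the fix, none remained, and no event that could be treatment-emergent was lost. This tests the logic; it is not a rate of affected events.

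**Size per patient.** About 300 patients randomized 1:1 is about 150 per arm; 1/150 = 0.67 percentage points.

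**The case against.** **Few real records fit.** This stands. Events are collected from consent, and screening lasts at most 28 days. For first dose on 15 Jun, consent is on or after 15 Jun − 28 days = 18 May, so apart from rescreened patients only a May stop is realistic, with a site that knew the stop month but not the start month. For cell (b), the safety follow-up visit is planned for Day 232, and 162 + 70 = 232, so it coincides with the end of the window. After a patient's end of trial only relevant serious events and events of special interest are reported (protocol section 5.3.6.2).

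**The effect on conclusions is slight.** This stands too. Safety analyses are descriptive and the same rule applies in both arms. A false event changes the drug-related proportion only if its causality is related or blank and the patient has no other related event.

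**Section 16.1.1.1 already settles the intent.** For cell (b) it does, but the programmer will code Appendix 2, and that cell omits the limit.

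**Discarding both dates protects against contradictory records.** This has force and limits the repair. Start July 2017 with stop May 2017 also reaches this branch, and treating it as worst case is defensible. Keeping the stop date without restriction would make that event not treatment-emergent. But 2017 to May 2017 is not contradictory; the imputation creates the conflict.

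**Stronger readings.** A reader might infer that events with a missing start and an early stop drop out of the Period 1 tables, because section 16.1.1.1 places some events as "treatment-emergent in the period of the last injection of trial medication". That clause covers only events whose status cannot be defined, and Appendix 2 explicitly classifies a missing start with a stop on or after first dose. A reader might also fault the missing-start, known-stop cell for having no upper limit. There the start cannot be shown to lie after the window, so the worst-case rule properly applies.

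**Conclusion.** The point holds for two cells: partial start with partial stop, and partial start with missing stop. In each, the stated rule contradicts the definition in section 16.1.1.1 and neighbouring cells of the same table, and the worst-case rule does not excuse it because the recorded parts settle the status.

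The importance is low. The error can only add treatment-emergent events, and each affected patient moves an arm's incidence by at most about 0.7 points. The documents give no frequency of partial dates, so the number of events cannot be estimated, but the collection rules suggest very few. A reader might infer that the safety comparison or the drug-related endpoint is materially inflated; the documents do not support that. The conclusion rests on a literal reading of Appendix 2. The calendar dates are illustrative.

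**What to change.** **Cell (a), partial start and partial stop.** Where the start was imputed to the first-dose date, the imputed latest possible stop is before first dose, and the earliest date allowed by the recorded start is not after that stop, treat only the start as missing, keep the imputed stop, and classify the event as not treatment-emergent. Records whose recorded start lies wholly after the stop may stay under the worst-case rule.

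**Cell (b), partial start and missing stop.** Impute the start as in the cells above. If it is later than the last dose + 70 days, the event is not treatment-emergent; otherwise it is.

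The cost is two lines of SAP text and a small programming change, with no new data. The downside is slightly fewer assumed treatment-emergent events.

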APPENDIX 3. EMA SOC ORDER FOR PRESENTATION OF THE AE IN THE TABLES.**Order System Organ Class**

- 0 Uncoded
- 1 Infections and infestations
- 2 Neoplasms benign, malignant and unspecified (incl cysts and polyps)
- 3 Blood and lymphatic system disorders
- 4 Immune system disorders
- 5 Endocrine disorders
- 6 Metabolism and nutrition disorders
- 7 Psychiatric disorders
- 8 Nervous system disorders
- 9 Eye disorders
- 10 Ear and labyrinth disorders
- 11 Cardiac disorders
- 12 Vascular disorders
- 13 Respiratory, thoracic and mediastinal disorders
- 14 Gastrointestinal disorders
- 15 Hepatobiliary disorders
- 16 Skin and subcutaneous tissue disorders
- 17 Musculoskeletal and connective tissue disorders
- 18 Renal and urinary disorders
- 19 Pregnancy, puerperium and perinatal conditions
- 20 Reproductive system and breast disorders
- 21 Congenital, familial and genetic disorders
- 22 General disorders and administration site conditions
- 23 Investigations
- 24 Injury, poisoning and procedural complications
- 25 Surgical and medical procedures
- 26 Social circumstances
- 27 Product issues

Document: \\ieedc-nas01a:\Boehringer_Ingelheim\BI_695501\XXA39605\Biostatistics\Documentation\SAP\15
-v2.0\BI 1297.12 SAP v2.0 31JAN2018.docx

Author: Version Number: 2.0
Version Date: 31JAN2018

Template No: CS_TP_BS016 Revision 4
Effective Date: 01Apr2016

Reference: CS_WI_BS005

APPENDIX 4. FILES ATTACHED TO SAP

Current BlcMQs Administration site reaction

Cut-off implementation document: BI1297_12_cut_off_v1.3_19SEP2017

Document: \\ieedc-nas01a:\Boehringer_Ingelheim\BI_695501\XXA39605\Biostatistics\Documentation\SAP\15
-v2.0\BI 1297.12 SAP v2.0 31JAN2018.docx

Author: Version Number: 2.0
Version Date: 31JAN2018

Template No: CS_TP_BS016 Revision 4
Effective Date: 01Apr2016

Reference: CS_WI_BS005

APPENDIX 5. LABORATORY ASSESSMENTS

Laboratory parameter	SI unit	US unit
Serum chemistry		
Creatinine	umol/L	mg/dL
Alkaline phosphatase	IU/L	IU/L
Aspartate aminotransferase (AST)	IU/L	IU/L
Alanine aminotransferase (ALT)	IU/L	IU/L
Gamma glutamyl transpeptidase (GGT)	IU/L	IU/L
Total bilirubin	umol/L	mg/dL
Direct bilirubin	umol/L	mg/dL
Glucose	mmol/L	mg/dL
Total cholesterol	mmol/L	mg/dL
Total protein	g/L	g/dL
Sodium	mmol/L	mEq/L
Potassium	mmol/L	mEq/L
Chloride	mmol/L	mEq/L
Calcium	mmol/L	mg/dL
Albumin	g/L	g/dL
Hematology		
Hemoglobin	g/L	g/dL
Hematocrit	V/V	%
Erythrocyte	10 ¹² /L	10 ⁶ /uL
Platelets	10 ⁹ /L	10 ³ /uL
White blood cells	10 ⁹ /L	10 ³ /uL
Lymphocytes	10 ⁹ /L	10 ³ /uL
Neutrophils	10 ⁹ /L	10 ³ /uL
Urinalysis		
Protein	g/L	g/dL
Glucose	mmol/L	mg/dL
Blood	N/A	N/A

Document: \\ieedc-nas01a:\Boehringer_Ingelheim\BI_695501\XXA39605\Biostatistics\Documentation\SAP\15
-v2.0\BI 1297.12 SAP v2.0 31JAN2018.docx

Author: Version Number: 2.0
Version Date: 31JAN2018

Template No: CS_TP_BS016 Revision 4
Effective Date: 01Apr2016

Reference: CS_WI_BS005

Copyright © 2009, 2010, 2012, 2016

All rights reserved.

The contents of this document are confidential and proprietary to
reproduction is strictly prohibited.

Unauthorized use, disclosure or

APPENDIX 6. SAS CODE FOR DIFFERENCE IN PROPORTION CIs

```
%let K=1000000; /*number of simulation*/
%let alpha=0.05; /*confidence level*/

proc IML;
  /*create theta and vartheta*/
  theta={&G. &Z.}; print theta; /*create theta vector*/
  vartheta={&VARG. &COVGZ. , &COVGZ. &VARZ.}; print vartheta; /*create
vartheta vector*/

  /*Create Xc the cholesky decomposition of Vartheta*/
  Xc = t(root(Vartheta));

  /*create X random normal vector*/
  call randseed(456); /* set random number seed */
  X = j(&K.,2); /* allocate the X vector */
  call randgen(X,"Normal");

  /*Write X matrix in a sas dataset called X*/
  X1=X[,1];
  X2=X[,2];
  create X var{X1 X2};
  append;
  close X;

  /*Calculate Y = X %% Xc*/
  Y=X*Xc;

  /*G,Z*/
  G=Y[,1]+Theta[1,1];
  Z=Y[,2]+Theta[1,2];
  DELTA=(1/(1+exp(-(G+Z))))-(1/(1+exp(-Z)));
  call sort(DELTA);

  LOW=DELTA[round(&k.*(&alpha./2))]; print low;
  UP=DELTA[&K.-round(&k.*(&alpha./2))]; print up;

quit;
```

Document: \\needc-nas01a:\Boehringer_Ingelheim\BI_695501\XXA39605\Biostatistics\Documentation\SAP\15
-v2.0\BI 1297.12 SAP v2.0 31JAN2018.docx

Author: Version Number: 2.0
Version Date: 31JAN2018

Template No: CS_TP_BS016 Revision 4
Effective Date: 01Apr2016

Reference: CS_WI_BS005

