7.7 DETERMINATION OF SAMPLE SIZE

To perform the equivalence test BI 695501 versus US-licensed Humira with $\geq 85\%$ power, approximately 300 patients are needed for this comparison (FAS).

For the calculation of the sample size a meta-analysis on Week 16 data of the REVEAL and CHAMPION trials ([R14-4849](#), [R14-4898](#)) was performed. This meta-analysis revealed a risk difference of 64.2% and a 95% CI (60.4% to 67.9%). [Table 7.7: 1](#) shows the information used in the meta-analysis.

The classical 95-50-95 approach would give a non-conservative acceptance margin of 30.2% for the risk difference preserving 50% of the Humira effect.

Calculation of a conservative equivalence margin

Preserve 70% of the lower confidence limit (lcl) 60.4% (obtained from the meta-analysis) of the historical effect over placebo. Equivalence margin = $(1 - \text{preserved proportion}) * \text{lcl}$, $(1-0.7)*60.4\% = 18\%$.

Table 7.7: 1 CHAMPION and REVEAL results

Humira versus Placebo	Treatment			Placebo		
	Events	Total	%	Events	Total	%
CHAMPION	86	108	79.6%	10	53	18.9%
REVEAL	578	814	71%	26	398	7%

The weighted mean response rate is assumed to be the true response rate of 72%. This sample size is based on an assumed treatment difference in proportions of patients with PASI 75 at Week 16 of 0%, a standard proportion of 72% and an equivalence margin of 18%. At a power of 85% the sample size would be 288.

[Table 7.7: 2](#) presents the sample size at different margins and different power.

Table 7.7: 2 Sample size according to different scenarios

Assumed true response rate (RR)	Margin	Confidence level (two-sided)	Power	Sample Size [#] Equivalence
72%	15%	95%	75%	340
72%	15%	95%	80%	366
72%	15%	95%	85%	414
72%	15%	95%	90%	572
72%	18%	95%	75%	234
72%	18%	95%	80%	256
72%	18%	95%	85%	288
72%	18%	95%	90%	330
72%	20%	95%	75%	188
72%	20%	95%	80%	200
72%	20%	95%	85%	228
72%	20%	95%	90%	262

[#] Allocation ratio 1:1

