15.1.3. PRIMARY ANALYSIS OF PRIMARY EFFICACY VARIABLE

The primary efficacy analysis will be performed for the FAS.

The primary objective of this trial is to test the hypothesis that BI 695501 and US-sourced Humira are equivalent.

The test for equivalence will be performed with respect to BI 695501 versus US-sourced Humira.

The hypotheses for the equivalence test can be written as follows:

- H_0 : Difference in PASI 75 response rates at Week 16 (BI 695501 minus US-sourced Humira) is less than -18.0% or more than 18.0%
- H_1 : Difference in PASI 75 response rates at Week 16 (BI 695501 minus US-sourced Humira) is within [-18.0%, 18.0%]

To conclude equivalence, the two-sided 95% CI of the difference in PASI 75 response rate (BI 695501 – Humira) rounded to 1 decimal place has to be fully within the equivalence limits of $\pm 18.0\%$.

The primary analysis of the difference in PASI 75 response rates at Week 16 will be based on logistic regression with subsequent transformation of the estimated parameters to the difference in proportions.

The estimates from the logistic regression are on the logit scale, and the difference in proportions will be calculated as the difference between the predicted probabilities in the treatment groups on the original scale, with the variance calculated using the cumulative distribution function method of Reeve (Reeve 2016).

The statistical model can be described as follows:

(M1) $\text{Logit}(\text{response to treatment at Week 16}) = \text{Treatment} + \text{Baseline PASI} + \text{Prior exposure to a biologic agent} + \text{random error}$

This model includes fixed, categorical effects of:

- Treatment (BI 695501 versus US-sourced Humira)

Document: \\ieedc-nas01a:\Boehringer_Ingelheim\BI_695501\XXA39605\Biostatistics\Documentation\SAP\15-v2.0\BI 1297.12 SAP v2.0 31JAN2018.docx

Author:

Version Number:

2.0

Version Date:

31JAN2018

Template No: CS_TP_BS016 Revision 4
Effective Date: 01Apr2016

Reference: CS_WI_BS005

- Prior exposure to a biologic agent (Yes versus No)

and continuous effect of:

- Baseline PASI

The random error is assumed to be binomially distributed.

The analysis will consist of the following four steps:

STEP 1: Starting from the incomplete dataset, data imputation method are applied (described in section 15.1.2) to generate 1000 completed datasets.

STEP 2: Calculation of difference in proportion based on adjusted PASI 75 responders

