The adjusted proportions of subjects with PASI 75 response in each groups at Week 16 are estimated from the logistics regressions on the logit scale, on each of the 1000 completed datasets.

The difference in proportions is calculated as the difference between the probabilities predicted by the model for both treatment groups on the original scale at Week 16.

STEP 3: Calculation of confidence intervals based on cumulative distribution function method of Reeve

The risk-difference confidence intervals are calculated on each completed datasets using the risk differences calculated in STEP 2) and the cumulative distribution function method of Reeve (Reeve 2016) with 1,000,000 simulations.

STEP 4: Computation of the final confidence interval

The estimated risk differences from STEP 2, and estimated standard errors back calculated using STEP 3 confidence intervals are combined using Rubin's Rules into the final confidence interval.

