15.1.3.2. Calculation of confidence interval (STEP 3 details)

The difference in proportion at Week 16 is produced in STEP 1.

The Week 16 confidence interval for the estimated difference in proportion are produced using the cumulative distribution function method of Reeve (Reeve 2016).

The SAS code to implement the method is provided in APPENDIX 6 and required as input:

1. Variance (g) is directly provided by SAS PROC GENMOD Empirical Standard Error Estimates.
2. $Cov(b_i, b_j)$ and $Cov(\gamma, b_i) \forall i, j \in [0; k]$ are directly provided by SAS PROC GENMOD Covariance Matrix (Empirical).
3. Variance (z) will be calculated using the formula:

$$Var(z) = Var\left(b_0 + b_1x_1^* + \dots + b_kx_k^*\right) = \sum_{i,j=0}^k x_i^* x_j^* Cov(b_i, b_j) \text{ where } x_0^* = 1$$

4. Covariance (g,z) will be calculated using the formula:

$$Cov(g, z) = Cov\left(\gamma, b_0 + b_1x_1^* + \dots + b_kx_k^*\right) = \sum_{i=0}^k x_i^* Cov(\gamma, b_i)$$

Then VarTheta is equal to $\begin{pmatrix} Var(g) & Cov(g, z) \\ Cov(g, z) & Var(z) \end{pmatrix}$

15.1.3.3. Computation of the final confidence interval with missing data method (NRI+MI) (STEP 4 details)

STEPS 1 and 2 are repeated on each imputed dataset produced by the multiple imputation method (fixed to 1000 datasets).

Estimated risk difference ($RD_{estimated}$) per imputed datasets is calculated using STEP 1.

Using Lower and Upper bounds calculated with Reeve's method per imputed datasets in STEP 2, and assuming that risk difference is normally distributed, the estimated standard error ($SE_{estimated}$) is calculated as:

$$SE_{low} = (RD_{estimated} - \text{Lower Bound}) / (z_{\alpha/2})$$

$$SE_{up} = (\text{Upper bound} - RD_{estimated}) / (z_{\alpha/2})$$

Where $z_{\alpha/2} = 1.96$ for 95% CI bounds

$$SE_{estimated} = \text{mean}(SE_{up}, SE_{low}).$$

The couple ($RD_{estimated}, SE_{estimated}$) per imputed dataset is then combine using Rubin's Rules to produce the final confidence interval.

The following SAS code will be used to combine the results:

Document: \\eedc-nas01a:\Boehringer_Ingelheim\BI_695501\XXA39605\Biostatistics\Documentation\SAP\15-v2.0\BI 1297.12 SAP v2.0 31JAN2018.docx

Author: Version Number: 2.0
Version Date: 31JAN2018

Template No: CS_TP_BS016 Revision 4
Effective Date: 01Apr2016

Reference: CS_WI_BS005

```
proc mianalyze data=data_RD_SE_per_MI_dataset;  
  modeleffects RD_ESTIMATE;  
  stderr RD_SE;  
run;
```

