15.2.3.1. PASI 75, sPGA and DLQI analysis

The risk difference will be estimated using the method of Reeve with a 95% significance level (see Section 15.1.3).

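### Appendix 6 appears to apply the Cholesky factor the wrong way round: the primary CI would not be a 95% interval, and planned power falls from about 87% to about 80–81%

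*SAP*

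**What the plan says.** SAP 15.1.3.2 defines VarTheta as the 2×2 covariance matrix of g (log odds ratio, BI 695501 against Humira as reference) and z (the Humira linear predictor). For the interval it points to the appendix: "The SAS code to implement the method is provided in APPENDIX 6 and required as input". Appendix 6 loads the matrix as "vartheta={&VARG. &COVGZ. , &COVGZ. &VARZ", sets the factor with "Xc = t(root(Vartheta", fills X with 1,000,000 rows of two independent standard normals, and computes `Y=X*Xc;`. After adding the point estimates, each row gives a risk difference through "DELTA=(1/(1+exp(-(G+Z))))-(1/(1+exp(-Z" (brackets cut in both code excerpts). The 2.5% and 97.5% points are the limits.

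In SAP 15.1.3, Step 4, the "estimated standard errors back calculated using STEP 3 confidence intervals are combined using" Rubin's rules. The final interval, "rounded to 1 decimal place has to be fully within the equivalence limits of" ±18.0%, decides equivalence. SAP 15.2.3.1 uses the same method for the binary secondary endpoints: "The risk difference will be estimated using the method of Reeve with a 95% significance level". Protocol 7.7 plans on 72% in both arms and a margin of 18%: "At a power of 85% the sample size would be 288". It aims for about 300 patients and at least 85% power.

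**The concern.** A row of independent normals multiplied on the right by M has covariance M'M. If ROOT() returns the upper factor U, with U'U = VarTheta, then M has to be U. The code uses U', so the draws have covariance UU', a different matrix. A transposed factor suits column vectors, but this code works with rows, and no later line corrects it.

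Nothing else in the SAP supplies a standard error for the primary decision, so the error passes straight into the equivalence CI and into the Week 24 PASI 75, sPGA and DLQI intervals. Two things are at stake. The sponsor loses power. The two arms are also treated unequally: the same pair of response counts can fail with BI 695501 as the lower arm and pass with it as the higher arm.

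**Working it through.** **Inputs.** 72% in both arms, margin 18%, two-sided 95% CI, N=288 or 300, 1:1 (Protocol 7.7). Step 4 SE and one-decimal rule (SAP 15.1.3 and 15.1.3.3). Code from Appendix 6. Assumed: ROOT() returns the upper factor, no covariate effect, negligible imputation variance.

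**1. The plan's own sample size.** Per arm, 2p(1−p)(z₀.₉₇₅ + z₀.₉₂₅)²/margin² = 0.4032 × (1.960 + 1.440)²/0.0324 = 143.8. Rounded up this is 144, or 288 in total, which matches Protocol 7.7.

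**2. Covariance simulated by the code.** Write VarTheta = [[a, c],[c, b]]. Then UU' has Var(g) = a + c²/a, Var(z) = b − c²/a and covariance (c/√a)·√(b − c²/a). At 108/150 in both arms, v = 1/(150 × 0.72 × 0.28) = 0.0331, so a = 2v, c = −v, b = v.

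| | Var(g) | Cov | Var(z) |
|---|---|---|---|
| Intended | 0.066 | −0.033 | 0.033 |
| As coded | 0.083 | −0.017 | 0.017 |

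A run of 1,000,000 draws confirmed both rows; using `root` without the transpose reproduces VarTheta.

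**3. Effect on the SE.** To first order, with w = p(1−p) and subscripts 1 for BI 695501 and 0 for Humira, Var(difference) = w₁²Var(g) + 2w₁(w₁−w₀)Cov + (w₁−w₀)²Var(z). At equal rates only Var(g) counts, so the SE is inflated by √(0.083/0.066) = √1.25 = 1.118: 0.2016 × √0.0827 = 5.80 points against 0.2016 × √0.0661 = 5.18. The full simulated limits give 5.77 against 5.18. With Humira at 108/150 and the Step 4 SE:

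| BI 695501 minus Humira (points) | −18 | −6 | 0 | +6 | +10 | +12 | +18 |
|---|---|---|---|---|---|---|---|
| SE coded / SE correct | 1.21 | 1.16 | 1.115 | 1.05 | 1.01 | 0.98 | 0.91 |

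**4. A decision that changes.** For 98/150 on BI 695501 against 108/150 on Humira (−6.7 points), the correct CI is (−17.1, 3.8), equivalent. The coded CI is (−18.8, 5.5), not equivalent. With the counts swapped, the coded CI is (−4.5, 17.8), equivalent. With Humira at 108, decisions differ only at 97, 98 or 99 BI 695501 responders.

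**5. Power at 72%/72%.** Normal approximation: 2Φ((0.18 − 1.96·SE_CI)/SE_true) − 1. At N=300, SE_true = 0.0518.
- Correct: 2Φ(3.472 − 1.960) − 1 = 86.9%.
- Coded: 2Φ(3.472 − 1.960 × 1.118) − 1 = 2Φ(1.281) − 1 = 80.0%.

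Binomial enumeration with the one-decimal rule gives 87.5% falling to 80.9% at N=300 (80.3% with a linearised SE), and 85.8% to 78.1% at N=288. The coded interval needs about N=330 for 85%. At other true rates with N=300: 81.8% to 73.2% at 65%/65%, and 94.6% to 90.4% at 80%/80%.

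**6. Error rates at the margins and coverage (N=300, Humira 72%).**

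| True difference | False equivalence, correct → coded | Coverage, correct → coded |
|---|---|---|
| −18 (54% vs 72%) | 2.5% → 1.3% | 94.7% → 98.1% |
| 0 | not applicable | 94.8% → 96.9% |
| +18 (90% vs 72%) | 2.6% → 3.0% (linearised 2.7% → 3.4%) | 95.1% → 93.0% |

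**The case against.** Four points can be made in the plan's favour.

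- **The premise is external.** The documents do not say which triangle ROOT() returns. If it were the lower factor, the code would be right and power would stay at about 87%. This stands as a condition on the finding.
- **The printed line may be damaged.** The comment above the product writes the multiplication with an odd double percent sign. A transpose mark after `Xc` could have been lost, and restoring it would make the code correct. This is possible but unlikely: the asterisk in that line survived, and the block writes its transpose as `t()`.
- **The error is mostly conservative.** At the planning values about 7% of trials move from pass to fail and essentially none the other way. The intervals become too narrow only beyond about +10 points, and with Humira at 108/150 equivalence has already failed by +8.7 points under either version. This is correct, so the main harm is to the sponsor. The slight rise in false equivalence at the upper margin remains.
- **The power figure is model-dependent.** It leaves out the M1 covariates and the imputation variance. A simulation with covariates, whose distribution had to be assumed, gave 86.3–86.5% falling to 79.3–79.4%. The loss is the same size. At 80%/80% power stays above 85%.

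None of these makes the printed code simulate VarTheta under the stated assumption.

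**Conclusion.** The concern holds, on the assumption that ROOT() returns the upper factor. As printed, Appendix 6 does not implement the interval that SAP 15.1.3.2 describes, and no other passage repairs it. At the protocol's planning values the SE is about 11–12% too large and power is about 80–81% at N=300 instead of about 87%, so the promised 85% is not delivered. The interval also lacks its nominal 95% level, and its error depends on which arm does better. The figures assume a two-arm model with negligible imputation variance, and the power shortfall depends on the true response rate. Because this code yields the only SE for the sole primary decision, it needs correcting before the result can be relied on.

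**What to change.** First check the production program, and the SAP page itself, for a transpose mark after `Xc` in the product line. If there is none, replace the factor line with `Xc = root(Vartheta);`, or keep it and use `Y = X*t(Xc);`. Add a programmed check that the sample covariance of Y reproduces VarTheta within simulation error; this is valid whichever triangle ROOT() returns. Correct Appendix 6 and re-run any primary or binary secondary output produced with the code as printed. The cost is one line of code, one check and a SAP correction, with no new data.
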